OCT	UNC Office of Clinical Trials (research.unc.edu/clinical-trials)
OHRP	Office for Human Research Protections
PHI	protected health information
PI	principal investigator
RCT	randomized controlled trial
REDCap	Research Electronic Data Capture system
RRS	Rumination Response Scale
SD	standard deviation
SE	standard error
S-EEfRT	Streamlined Effort Expenditure for Rewards Task
SHAPS	Snaith Hamilton Pleasure Scale – Self-Report
SHAPS-C	Snaith Hamilton Pleasure Scale – Clinician Administered
SOP	standard operating procedures
SRC	UNC Scientific Review Committee (research.unc.edu/clinical-trials/src)
STAI	State-Trait Anxiety Inventory
tACS	Transcranial alternating current stimulation
tDCS	Transcranial alternating current stimulation Transcranial direct current stimulation
TEPS	Temporal Experience of Pleasure Scale
TMS	Transcranial magnetic stimulation
TraCS	N.C. Translational and Clinical Sciences Institute (tracs.unc.edu)
tRNS	transcranial random noise stimulation
UNC	The University of North Carolina

1. Protocol Synopsis

Title	Augmenting single-session behavioral activation (BA) with delta-beta transcranial alternating current stimulation (tACS) for the treatment of depression				
Study Description	The purpose of this study is to examine whether concurrent transcranial alternating current stimulation (tACS) augments the effects of a single session behavioral activation (BA) treatment of depression. Following a series of clinical assessments, participants will perform a reward-based decision-making task while electroencephalography (EEG) is collected. Then, all participants will take part in a single-session 90-minute BA intervention; half of the participants will receive delta-beta tACS during the final 30 minutes of the session and half will receive an active sham stimulation. Participants will return two weeks later for another task-based EEG. Four weeks after the intervention session, they will receive self-report questionnaires via email to complete online.				
Specific Aims (objectives)	Aim 1 (PRIMARY). Evaluate the effects of delta-beta transcranial alternating current stimulation (tACS) on depression symptom severity from pre- to post-treatment.				
	Aim 2 (SECONDARY). Examine changes in goal-directed behavior during a reward-based decision-making task from pre- to post-treatment.				
	Aim 3 (SECONDARY). Investigate changes in delta-beta coupling during a reward-based decision-making task from pre- to post-treatment.				

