2.1. Background Information

Major depressive disorder (MDD) is a common and debilitating disorder characterized by heterogeneity and variability of treatment response (Fava et al., 1997; Friedrich, 2017). Behavioral activation (BA) is a treatment for MDD and depressive symptoms aimed at increasing engagement with pleasurable and mastery activities in line with an individual's identified values (Dimidjian et al., 2014; Mazzucchelli et al., 2009). Obstacles to treatment engagement, including time and resource limitations, often contribute to worse treatment outcomes and have led to consideration of single-session depression interventions (Gawrysiak et al., 2009; Schleider et al., 2022; Parra et al., 2019; Read et al., 2016 Wasil et al., 2021), and initial studies have largely found reductions in stress and depressive symptoms, as well as increases in self-reported agency following single-session BA interventions.

Additionally, recent findings have emerged that suggest non-invasive brain stimulation may be a particularly effective intervention for treatment-resistance. Guided by prior research from our lab, this study will investigate the effect of delta-beta transcranial alternating current stimulation (tACS) on response to single-session BA for depression. Coupling between low-frequency cognitive control signals in the delta frequency band (1-4 Hz)

Version 2

19 September 2022

emanating from prefrontal cortex and the amplitude of beta oscillations (15-30 Hz) in the primary motor cortex was found to be positively correlated with goal-directed behavior in our previous experiment (Riddle et al., 2022). Furthermore, individual differences in the strength of delta-beta coupling were negatively correlated with depressive symptoms in a sample that included patients within a major depressive episode.

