2.2. Scientific Rationale

This study is a randomized, sham-controlled interventional parallel-arm clinical trial. All participants will receive the same single-session BA intervention. Concurrent with the goal-directed phase of the BA intervention, participants will receive either delta-beta tACS or an active sham stimulation. All researchers involved in data collection and the participants receiving stimulation will be blind to the stimulation condition to reduce bias in the data collection process, i.e., double-blinding. A previous study in the lab found that depressed participants demonstrated reduced delta-beta coupling (Riddle et al., Cerebral Cortex 2022), and a study currently ongoing is testing the impact of delta-beta stimulation on performance during a reward-related decision-making task (NCT05084924). Moreover, another previous study recorded EEG during the S-EEfRT in patients with MDD. This study found that participants with MDD demonstrated reduced goal-directed behavior and reduced delta-beta coupling. This preliminary data provides strong evidence that stimulation delivered in a delta-beta pattern should be beneficial to reward-related behavioral outcomes that are the focus of BA. The proposed study will build on these findings to determine whether a BA intervention combined with targeted stimulation may lead to improved treatment outcomes in reward-related constructs.

3. Specific Aims

3.1. Aim 1

(PRIMARY) Evaluate the effects of delta-beta transcranial alternating current stimulation (tACS) on depression symptom severity from pre- to post-treatment.

3.2. Aim 2

(SECONDARY) Examine changes in goal-directed behavior during a reward-based decision-making task from pre- to post-treatment.

3.3. Aim 3

(SECONDARY) Investigate changes in delta-beta coupling during a reward-based decision-making task from pre- to post-treatment.

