4.2. Experimental Design

All participants will receive the single-session 90-minute BA intervention. Participants will be randomized to either receive either cross-frequency transcranial alternating current stimulation (tACS) or an active sham.

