8.3. Aim-Specific Plans

Plans for Aim 1 (PRIMARY).

Treatment response will be calculated as the depression (HDRS) scores from pre- to post-treatment. A two-way analysis of variance (ANOVA) will be performed using within-participant factor of time (before or after treatment), between-participant factor stimulation type (delta-beta tACS, active-sham), and the interaction between time and stimulation type. We hypothesize to find an interaction between time and stimulation type. Post hoc differences will be investigated. We hypothesize that the predicted interaction will be driven by a decrease in depressive symptoms for delta-beta tACS compared to the active-sham. Sensitivity analyses will be conducted to evaluate the specificity of these effects: a similar analysis with anxiety symptoms as the dependent variable and we do not expect that delta-beta tACS will have any effect on anxiety symptoms.

Further, we will conduct exploratory generalized linear mixed models will be conducted to examine potential confounds on treatment effect (e.g., age, sex, baseline depressive symptoms).

Plans for Aim 2 (SECONDARY).

Delta-beta phase amplitude coupling will be calculated between the phase of delta oscillations (2-3 Hz) in prefrontal electrodes (FCz and surrounding electrodes) and the amplitude of beta oscillations (15- 25 Hz) in left motor electrodes (C3 and surrounding electrodes). The instantaneous phase and amplitude of these oscillations will be calculated by averaging the signal in these two regions of interest, band-filtering the signal to the specified range, and then performing the Hilbert transform on the signal. Phase-amplitude coupling (PAC) is then calculated by creating a hybrid signal using the amplitude of beta oscillations in left motor electrodes and the phase of delta oscillations in prefrontal electrodes:

[†][1] www.consort-statement.org , [2] www.strobe-statement.org, [3] www.icmje.org

^[4] Wasserstein RL, et al. (2016), The ASA's Statement on p-Values, *The American Statistician*, 70:2, 129-133.

^[5] Wasserstein RL, et al. (2019), Moving to a World Beyond p < 0.05, *The American Statistician*, 73:sup1, 1-19.

^[6] Amrhein, et al. (2019), Scientists rise up against statistical significance, *Nature* 567, 305-307.

^[7] Editorial (2019) It's time to talk about ditching statistical significance: ... *Nature* 567, 283-283.

$$PAC = \left| \frac{\sum_{t=1}^{N} M * e^{i\theta}}{N} \right|$$

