Exploratory analyses are planned only if effects are seen on depressive symptoms (Aim 1). If so, we plan to explore the potential effects specific to anhedonia symptoms. Treatment response will be calculated as the change in anhedonia (SHAPS-C) scores from pre- to post-treatment. A two-way analysis of variance (ANOVA) will be performed using within-participant factor of time (before or after treatment) and between-participant factor stimulation type (delta-beta tACS, active-sham). We hypothesize to find an interaction between time and stimulation type. Post hoc differences will be investigated. We hypothesize that the predicted interaction will be driven by a decrease in anhedonia symptoms for delta-beta tACS compared to the active-sham.

Further, we will conduct exploratory generalized linear mixed models will be conducted to examine potential confounds on treatment effect (e.g., age, sex, baseline non-anhedonic depressive symptoms).

Exploratory analyses with anhedonia symptoms will not be conducted if effects for overall depressive symptoms (Aim 1) are not found.

Planned Interim Analyses

No interim analyses will be performed.

The experiment proposed here will utilize a parallel arm design, and primary analyses will use a repeated-measures ANOVA with one within-participant factor (before and after treatment) and one between-participants factor (deltabeta, placebo). With an average effect size of 0.286 partial-eta square estimated from existing literature on single session BA, we estimate that we need at least 15 participants per group to achieve 80% statistical power. Using a conservative estimate of 0.5 correlation between estimates, we still reach ~99% power with 40 participants (Figure 3). Data will be collected until we reach 40 participants. Given the similarity in stimulation methodology between the current experiment and our previous experiment (Riddle et al., 2021), we anticipate adequate levels of power for hypothesis testing with 40 participants. Moreover, other studies of combined psychotherapy and stimulation have reported similar sample sizes (Neacsiu et al., 2022).

[figure not shown]

Figure 3. Power analysis for impact of BA + tACS on depressive symptoms with ANOVA.

10. Data Capture and Database Management

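### The 80% and ~99% power figures rest on an effect of BA, not on the tACS-versus-sham difference that the primary test examines

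*Combined protocol and SAP*

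**What the plan says.** The Synopsis gives the purpose of the study as to "examine whether concurrent transcranial alternating current stimulation (tACS) augments the effects of a single session behavioral activation (BA) treatment of depression". Section 4.2 makes BA common to both arms: "All participants will receive the single-session 90-minute BA intervention". Only stimulation is randomised, delta-beta tACS or active sham.

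Section 8.3 (Aim 1) tests the interaction of time and stimulation type on the HDRS in a two-way ANOVA and gives its direction: "We hypothesize that the predicted interaction will be driven by a decrease in depressive symptoms for delta-beta tACS compared to the active-sham".

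The text of Section 9 (printed after the statement that there are no interim analyses) gives one numerical effect size: "With an average effect size of 0.286 partial-eta square estimated from existing literature on single session BA". It concludes that 15 per group are needed for 80% power. Then, with a correlation of 0.5, it adds: "we still reach ~99% power with 40 participants". Two arguments without a number follow. One is that the stimulation method resembles that of an earlier experiment, from which "we anticipate adequate levels of power for hypothesis testing with 40 participants". The other is that other trials combining psychotherapy with stimulation had samples of similar size.

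**The concern.** The effect size belongs to a different comparison. Section 2.1 summarises the single-session BA literature without mentioning stimulation: "initial studies have largely found reductions in stress and depressive symptoms, as well as increases in self-reported agency following single-session BA interventions". The documents do not say whether 0.286 is a pre-post effect or an effect of BA against a control. Neither is the tested contrast. When both arms receive BA, its effect appears in the main effect of time, and the interaction isolates what tACS adds.

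No other place in the documents supplies the missing number:

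- The earlier stimulation experiment cited in Section 9 comes without an effect size, and the reference list gives it a title about cognitive control.
- Section 2.2 cites work in progress on a behavioural outcome: "a study currently ongoing is testing the impact of delta-beta stimulation on performance during a reward-related decision-making task".
- Section 5.7 mentions a concluded trial of delta-beta tACS against active sham, but only for its blinding questionnaire.

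The two power figures are the only quantitative justification of N for the primary hypothesis. A reader would take from them that the primary test is almost certain to detect the tACS effect, and nothing in the documents supports that. The text of Section 9 also does not say what difference between tACS and sham 40 participants can detect.

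**Working it through.** **Inputs.** Partial eta-squared 0.286, 15 per group for 80%, 40 participants for ~99% and correlation 0.5 come from Section 9. The threshold of 0.05 comes from Section 8.1; sidedness is not stated, but the 1-df interaction F test is equivalent to a two-sided t-test on change scores. The 20 per arm and the expectation of at least 30 with complete data come from the Synopsis.

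**Conversion.** f² = 0.286/(1 − 0.286) = 0.286/0.714 = 0.4006, so f = 0.633. With two equal groups compared on change, d = 2f = 1.27 SD of HDRS change.

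**The plan's own figures.** Power is from the noncentral F distribution with 1 and N − 2 df.

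| Reading of 0.286 | Noncentrality | N = 30 | N = 40 |
|---|---|---|---|
| Interaction on change scores | f²·N | 91.7% | 97.4% |
| Same, with N − 2 | f²·(N − 2) | 89.8% | 96.7% |
| Between-subject factor, ρ = 0.5 | f²·N·2/(1 + ρ) | 97.1% | 99.4% |
| Interaction, correlation added separately, ρ = 0.5 | f²·N·2/(1 − ρ) | >99.9% | >99.9% |
| 0.286 entered as f² itself, change scores | 0.286·N | 80.7% | 90.9% |

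The ~99% with 40 can be approached in several ways. The 80% with 15 per group is not reached when 0.286 is taken as partial eta-squared. It is reached if 0.286 is entered as f², but then 40 participants give 90.9%. None of the readings tried gives both figures. Section 9 attaches the 0.5 correlation only to the second figure, so the two may use different settings. This is a minor point. The main defect is the source of 0.286, whichever formula was used.

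**What the design can detect.** For the interaction, the noncentrality is N·d²/4, and partial eta-squared = (d/2)²/(1 + (d/2)²).

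- 40 analysed, 80% power: d = 0.91, partial eta-squared 0.17.
- 30 analysed, 80% power: d = 1.06, partial eta-squared 0.22.
- 40 analysed, 99% power: d = 1.39, partial eta-squared 0.33.

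Here d is in SDs of HDRS change. With equal variances and the plan's correlation of 0.5, SD of change = SD·√(2(1 − 0.5)) = SD, so the same values apply to the raw HDRS SD.

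**Power at smaller differences.** The documents give no tACS increment, so each d below is an assumption.

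| Assumed d | 40 analysed | 30 analysed |
|---|---|---|
| 0.3 | 15.2% | 12.5% |
| 0.5 | 33.8% | 26.2% |
| 0.63 | 49.6% | 38.8% |
| 0.8 | 69.3% | 56.2% |
| 1.0 | 86.9% | 75.3% |

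The row at 0.63 ties the assumption to the plan's input. If 0.286 is a one-group pre-post effect, BA's change is √0.4006 = 0.63 SD, and an increment of 0.63 means that tACS doubles it. If 0.286 is BA against control, BA's effect is 1.27 SD, and an increment of 0.63 means that tACS adds half as much again.

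**The case against.** The strongest reply is that nothing in the conduct or analysis of the trial depends on these figures. Section 8.1 already treats large p-values as inconclusive, and Section 2.1 looks ahead to larger trials. The arithmetic behind ~99% is roughly recoverable, and 80% with 15 per group is lower than 0.286 would imply, so the plan did not inflate that figure. Figure 3 is captioned as power for BA plus tACS and cannot be seen in the text available. Section 9 also cites similar sample sizes in other combined trials. Finally, 30 analysed may be too pessimistic: Section 5.6 provides 10 spare codes for participants who discontinue and says collection continues to 40.

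Much of this stands as a limit. The harm is confined to the justification of N, and the figures do not show that the trial is underpowered. The case of 30 is a sensitivity case: the Synopsis floor concerns completion of every part of the protocol, so more may have HDRS data. On the other hand, Section 7.7 rules out replacing participants who withdraw after receiving any of the intervention.

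The core is untouched. Whatever Figure 3 shows, the text names BA literature as the source of the effect size. Precedent for a sample size supplies no effect size. N = 40 might be defended on feasibility, but Section 9 instead claims 80% and ~99% power.

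**Conclusion.** The concern holds, and Section 9 is wrong as written. The stated powers are not powers for the primary hypothesis, because 0.286 does not estimate the time by stimulation interaction and the documents contain no estimate that does. Carried over to that interaction, it would require tACS to beat sham by 1.27 SD of HDRS change, an increment that no part of the plan supports. At two-sided 0.05 with equal arms, the design has 80% power for 0.91 SD with 40 analysed and for 1.06 SD with 30. Below that, power falls quickly, to 34% at an assumed 0.5 SD with 40. The conclusion about sourcing rests on the text alone; the power values at smaller differences rest on assumed increments.

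**What to change.** Withdraw both figures as statements of power for the tACS effect. Then do one of two things:

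- Give a tACS-versus-sham difference in HDRS change with its source, and recompute. The concluded trial mentioned in Section 5.7 is one place to look, if it recorded depression scores.
- State the detectable difference, for example: With 40 analysed, the time by stimulation test (two-sided 0.05) has 80% power for a between-arm difference of 0.91 SD of HDRS change. Give 1.06 SD with 30 analysed separately, as a sensitivity case.

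In either case, show power at smaller differences, labelled as assumptions, and state the formula, correlation and software settings behind every power figure that is kept. Revise Figure 3 only if it rests on 0.286.

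The cost is a rewording of Section 9 and a less favourable stated power. N = 40 and the planned ANOVA do not change.

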10.1. Software for Data Capture

The study data will be entered into a REDCap database developed by the study personnel. REDCap is a 21 CFR Part 11-compliant data capture system provided by the NC TraCS Institute at UNC. The data system includes password protection and internal quality checks, such as automatic range checks, to identify data that appear inconsistent, incomplete, or inaccurate. Study data will be entered directly from the source documents.

10.2. Responsibilities for Data Capture and Database Management

Data collection is the responsibility of the clinical trial staff at the site under the supervision of the site investigator. The investigator is responsible for ensuring the accuracy, completeness, legibility, and timeliness of the data reported.

All source documents should be completed in a neat, legible manner to ensure accurate interpretation of data.

Hardcopies of the study visit worksheets will be provided for use as source document worksheets for recording data for each participant enrolled in the study. Data recorded in the electronic case report form (eCRF) derived from source documents should be consistent with the data recorded on the source documents.

Clinical data (including adverse events (AEs), concomitant medications, and expected adverse reactions data) and clinical laboratory data will be entered into REDCap, a 21 CFR Part 11-compliant data capture system provided by the TraACS. The data system includes password protection and internal quality checks, such as automatic range checks, to identify data that appear inconsistent, incomplete, or inaccurate. Clinical data will be entered directly from the source documents.

10.3. Study Records Retention

According to the University of North Carolina at Chapel Hill's Archives and Record Management Services schedule for General Records Retention and Disposition Schedule, records will be kept for three years after the completion of the study or grant end date, whichever is later.

11. Collection and Management of Tissue Specimens

11.1. Use in Current and Future Studies

N/A

11.2. Sample Preparation

N/A

11.3. Record Keeping and Monitoring

N/A

11.4. Storage and Security

N/A

12. Safety Monitoring and Management

12.1. Risk / Benefit Assessment

Potential Risks: Risk of Confidentiality Breach: In the unlikely event of a breach of confidentiality, people might discover that an individual was involved in this research study. This is especially sensitive because the clinical population recruited for this study may be subjected to negative consequences caused by the stigma of mental disorders. Furthermore, some might not agree with the principle of participating in research or of changing natural

Version 2

Protocol Number <#> 19 September 2022

brain activity. To avoid breaches in confidentiality, study documents that contain personal information and including the informed consent document are kept in locked filing cabinets in locked rooms separate from any source documents containing participant dummy identifiers. The document that links study ID numbers to personal identifying information is encrypted and protected using a password-protected document on a secure server provided by UNC School of Medicine. All data is stored in locked cabinets inside locked offices; electronic data will be stored only on password-protected computers, and data encryption methods will be used during communication between investigators. Only study personnel will have access to the data. All study staff participate in annual human participant training that includes education about responsibilities to the minimize risk of confidentiality breach. Risk of Embarrassment: Self-report assessments contain questions regarding sensitive personal information. This risk is necessary in order to assess mood symptoms and associated psychopathology. Participants will be assured upon intake that only study personnel will see any clinical ratings and that self-identifying information will not be collected alongside HIPAA protected information.

Risk of Injury and Discomfort: The side effects of tACS are mild and transient; in fact, low intensity transcranial current stimulation, such as tACS, has been used for over a decade without any report of serious side effects (Antal, Alekseichuk et al. 2017). Furthermore, this stimulation mode has nothing to do with electroconvulsive therapy that applies many orders of magnitude higher stimulation current. Rather, transcranial current stimulation is so weak that it does not cause super-threshold activation of neurons ([name] and McCormick 2010). However, tACS does have some mild side effects, such as transient mild tingling, burning, or itching under the electrode sites. In our previous trial, participants from all three groups of stimulation reported either absent or mild side effects, and there was no difference between the groups with the exception of "flickering lights" (or phosphenes, p = 0.014) (Alexander, Alagapan et al. 2019). To monitor these mild side effects, we will be administering a stimulation questionnaire after each stimulation session to determine whether these effects were experienced and at what intensity. Research personnel present during these sessions will also check in with the participant periodically during the stimulation to see whether they are comfortable. If participant is experiencing severe discomfort (as determined by the questionnaire or by self-report), the stimulation will be stopped immediately.

Potential Benefits: This study has not been designed to benefit the individual participants. However, the knowledge gained from this study will contribute to understanding about the psychological and biological basis of depression. Furthermore, the results from this study might be used to inform future interventions using a combination of brief psychotherapy and non-invasive brain stimulation.

